5.4. Study Endpoint Descriptions

Table 2: Study Endpoints

Endpoint	Name	Description	Timeframe
Phase 1			
Phase 1 Primary	Safety	Frequency and severity of adverse events, changes in vital signs, laboratory assessments, Performance Status assessment, and immunological and inflammation assessments.	DLTs assessed from Study Day 1 through Day 28
Futility Check for go/no go decision to move to Phase 2:		Efficacy as measured by clinical improvement by OSCI. At least 2 out of 14 subjects must achieve at least 1 "Patient State" category improvement in Ordinal Score (OSCI)	Study Day 15
Phase 2			
Phase 2 Primary	Time to clinical improvement by OSCI	Time to clinical improvement measured by OSCI	Study Day 28
Phase 2 Secondary	Clinical status by OSCI	Ordinal scale by OSCI	Study Day 28
	Rate of clinical improvement by OSCI	Proportion of subjects who achieved clinical improvements by OSCI	Study Day 28
	Time to clinical improvement by NEWS2	Time to clinical improvement measured by NEWS2 Score	Study Day 28
	Rate of clinical improvement by NEWS2	Proportion of subjects who achieved clinical symptom improvement by NEWS2 Score	Study Day 28
	Rate of clearance of SARS-CoV-2	Proportion of subjects with clearance of SARS-CoV-2 from mucosal specimens (nasopharyngeal swab, oropharyngeal swab if available)	Study Day 28
	Time to clearance of SARS-CoV-2	Clearance of SARS-CoV-2 by rRT-PCR testing of mucosal samples (nasopharyngeal swab, oropharyngeal swab if available); negative results should be confirmed by same sample type at least 24 hours after the first negative result	Study Day 28

	Time to pulmonary clearance	Time to disappearance of virus from LRT specimen where it has previously been found (induced sputum if available, endotracheal aspirate if available)	Study Day 28
	Rate to pulmonary clearance	Proportion of subjects who had disappearance of virus from LRT specimens where it has previously been found.	Study Day 28
	Duration of hospitalization	Duration of hospitalization from time from hospitalization to medical discharge	Study Day 28
	Supplemental oxygen-free days	For subjects requiring supplemental oxygen, days with supplemental oxygen-free days	Study Day 28
	Proportion of subjects requiring ventilation	Proportion of subjects who need invasive or non-invasive ventilation	Study Day 28
	SOFA Score	Sequential Organ Failure Assessment (SOFA) score	Study Day 28

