- **Ventilatory Support:** For those subjects requiring ventilatory support or supplemental oxygen during the treatment period:
 - Supplemental oxygen-free days
 - Proportion of subjects developing respiratory failure requiring invasive or noninvasive mechanical ventilation.
- **SOFA Score:** For those subjects evaluated by Sequential Organ Failure Assessment (SOFA) scores from ICU admission through ICU discharge (for subjects requiring intensive care). Mean arterial pressure should be measured with an arterial line. See [Appendix A](#).
 - Organ support, according to the number of days within the 28 days starting from Day 1 when subjects do not receive specific forms of support:
 - a. Supplemental oxygen-free days
 - b. Renal replacement therapy-free days
 - c. Vasopressor-free days
 - d. Invasive or non-invasive mechanical ventilation free days
 - e. Organ support-free days (that is, days free of invasive mechanical ventilation, renal replacement therapy and vasopressors)
 - f. Extracorporeal circulation support-free days
- **Mortality Rate:** defined as the proportion of subjects who died by any cause.

Figure 2: Study Schema

[figure not shown]

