8. SELECTION AND WITHDRAWAL OF SUBJECTS

8.1. Subject Inclusion Criteria

1. Subject has confirmed positivity for SARS-CoV-2 as measured by rRT-PCR or other approved test to detect SARS-CoV-2 per institutional practice.
2. Subject is experiencing any symptom/clinical sign of COVID-19 illness or has a positive disease-related chest x-ray/CT scan at screening.
3. Subject is ≥ 18 years of age at the time of signing the Study informed consent form (ICF).
4. Subject understands and voluntarily signs the Study ICF prior to any study-related assessments/procedures are conducted.
5. Subject is willing and able to adhere to the study schedule and other protocol requirements.
6. $\text{SpO}_2 \geq 88\%$ on room air; oxygen is permitted as delivered by nasal cannula and/or face mask at any flow rate to achieve this SpO_2 . Subjects must have an $\text{SpO}_2 \geq 92\%$ if on supplementary oxygen.
 - *(Note: Once eligibility is confirmed, to initiate CYNK-001 treatment, an increase of supplemental oxygen of greater than or equal to 50% from baseline/screening resulting in oxygen use of greater than 8L -or- a change in mode of supplemental oxygen delivery with the intention to deliver oxygen more frequently requires consultation with the medical monitor)*
7. Ability to be off immunosuppressive drugs for 3 days prior to infusion, unless clinically indicated. Steroids are permitted if clinically indicated and at the discretion of the treating physician. If clinically indicated, careful consideration should be taken regarding the timing and tapering of high-dose steroids.
8. Female of childbearing potential (FCBP)* must not be pregnant and agree to not becoming pregnant for at least 28 days following the last infusion of CYNK-001. FCBP must agree to use an adequate method of contraception during the treatment period.
 - a. *FCBP is a female who: 1) has achieved menarche at some point, 2) has not undergone a hysterectomy or bilateral oophorectomy or 3) has not been naturally postmenopausal (amenorrhea following cancer therapy does not rule out childbearing potential) for at least 24 consecutive months (i.e., has had menses at any time in the preceding 24 consecutive months).
9. Male subjects must agree to use a condom during sexual contact for at least 28 days following the last infusion of CYNK-001, even if he has undergone a successful vasectomy.

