8.2. Subject Exclusion Criteria

1. Subject requires supplemental oxygen delivered by mechanical ventilation, either invasive or bilevel positive airway pressure.

[figure not shown]
2. Subject admitted to Intensive Care Unit / Pulmonary Acute Care Unit designated area with severe pulmonary pneumonia, ARDS or Sepsis.
3. Subject is pregnant or breastfeeding.
4. Subject has a history of chronic asthma requiring ongoing medical therapy or other chronic pulmonary disease that, at the discretion of the treating physician, would contraindicate participation in this study.
5. Subject has any other organ dysfunction [Common Terminology Criteria for AEs (CTCAE) Version 5.0 Grade 3] that will interfere with the administration of the therapy according to this protocol.
6. Subject has inadequate organ function as defined below at time of Treatment Eligibility Period:
 - a) Subject has aspartate aminotransferase (AST), alanine aminotransferase (ALT), or alkaline phosphatase $\geq 5 \times$ the upper limit of normal (ULN). (It is anticipated that the infection may impact liver.)
 - b) Estimated glomerular filtration rate (eGFR) < 30 mL/min/1.73 m² as calculated using the Modification of Diet in Renal Disease Study equation (Levey, 2006) or history of an abnormal eGFR < 60 . A decline of > 15 mL/min/1.73 m² below normal in the past year prior to infection. (It is anticipated that the infection may impact renal function.)
 - c) Subject has a bilirubin level > 2 mg/dL (unless subject has known Gilbert's Syndrome).
7. Subject has a known sensitivity or allergy to treatment additives or diluent substances of dimethyl sulfoxide (DMSO), PlasmaLyte A or human serum albumin (HSA). Please refer to investigational brochure (IB).
8. Subject has active autoimmune disease other than controlled connective tissue disorder or those who are not on active therapy.
9. Subject is immunocompromised, has known human immunodeficiency virus (HIV) positivity, or has actively been treated with immunosuppressive products prior to being infected with SARS-CoV-2.
10. Subject has known active malignancy, unless the subject has been free of disease for ≥ 3 years from the date of signing the ICF. Exceptions include the following noninvasive malignancies:
 - a. Basal cell carcinoma of the skin
 - b. Squamous cell carcinoma of the skin
 - c. Carcinoma in situ of the cervix
 - d. Carcinoma in situ of the breast
 - e. Incidental histological finding of prostate cancer (TNM stage of T1a or T1b)

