13.2 Efficacy Endpoints

The study includes the following efficacy endpoints:

- 1) Clinical status by OSCI at Day 28.
- 2) Clinical improvement by OSCI by Day 15.
- 3) Rate of clinical improvement by OSCI at Day 28. The rate is defined as the proportion of subjects who achieved clinical improvement by OSCI on or prior to Day 28.
- 4) Time to clinical improvement as measured by OSCI.
- 5) Time to clinical improvement by NEWS2. Time to clinical improvement by NEWS2 is defined as the time from the date of randomization (date of first dose of CYNK-001 for Phase 1) to the first date of clinical improvement by NEWS2. Clinical improvement by NEWS2 is defined as a 25% decrease compared to baseline in the NEWS2 Score. Subjects without clinical improvement by NEWS2 on or before Day 28 will be censored at Day 28.

- 6) Rate of clinical improvement by NEWS2 at Day 28. The rate is defined as the proportion of subjects who achieved clinical symptom improvement by NEWS2 Score on or prior to Day 28.
- 7) Rate of clearance of SARS-CoV-2 from mucosal specimens at Day 28. Rate is defined as the proportion of subjects with clearance of SARS-CoV-2 by rRT-PCR by two negative results at least 24 hours apart. Specimens included are nasopharyngeal swab and optional oropharyngeal swab.
- 8) Time to clearance of SARS-CoV-2 from mucosal specimens at Day 28. Clearance is defined as the time from the date of randomization to clearance of SARS-CoV-2 by rRT-PCR by two negative results at least 24 hours apart. Specimens included are nasopharyngeal swab and optional oropharyngeal swab.
- 9) Time to pulmonary clearance at Day 28. Clearance is defined as the time from randomization to the date of pulmonary clearance. This is defined as disappearance of virus from LRT specimen where it has previously been found (induced sputum and endotracheal aspirate if available).
- 10) Rate of pulmonary clearance at Day 28. Rate is defined as the proportion of subjects who had disappearance of virus from LRT specimens where it has previously been found.
- 11) Duration of hospitalization from date of hospitalization to date of medical discharge.
- 12) For subjects requiring supplemental oxygen, the days with supplemental oxygen-free up to Day 28.
- 13) Proportion of subjects who need invasive or non-invasive ventilation up to Day 28.
- 14) SOFA score for subjects admitted to the ICU from ICU admission to ICU discharge, up to Day 28.

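### Oxygen-free days and SOFA are summarised only in subjects who need oxygen or intensive care, groups that treatment can change, so the arms compared are not the randomised arms

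*SAP*

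**What the plan says.** **Oxygen-free days.** SAP 13.2 item 12 reads "For subjects requiring supplemental oxygen, the days with supplemental oxygen-free up to Day 28". Protocol Table 2 (section 5.4) carries the same restriction. Neither says when the need must arise. Protocol 6.9, repeated in section 11, places the endpoint under the heading "For those subjects requiring ventilatory support or supplemental oxygen during the treatment period", that is, Day 1 to Day 28. No value is assigned to a subject who never uses oxygen, and no rule is given for death.

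**SOFA.** SAP 13.2 item 14 reads "SOFA score for subjects admitted to the ICU from ICU admission to ICU discharge, up to Day 28". Protocol 6.9 and 11 restrict it in the same way. Exclusion criterion 2 (protocol 8.2) keeps out any "Subject admitted to Intensive Care Unit / Pulmonary Acute Care Unit designated area with severe pulmonary pneumonia, ARDS or Sepsis".

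**Ventilation.** Protocol 6.9 lists "Proportion of subjects developing respiratory failure requiring invasive or noninvasive mechanical ventilation" under the same conditional heading as oxygen-free days, and section 11 does likewise. Protocol Table 2 has "Proportion of subjects who need invasive or non-invasive ventilation" and SAP 13.2 item 13 has "Proportion of subjects who need invasive or non-invasive ventilation up to Day 28", both without restriction.

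**Entry on oxygen.** Inclusion criterion 6 (protocol 8.1) says that "oxygen is permitted as delivered by nasal cannula and/or face mask at any flow rate".

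**Analysis.** SAP 13.3 uses the ITT population for secondary endpoints unless something else is specified, tests no formal hypothesis on them and treats their p-values as informative. SOFA is tabulated descriptively by arm, with last observation carried forward for missing values. SAP 15 records that the trial was closed with 7 subjects dosed, all in Phase I.

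**The concern.** Randomisation balances the arms at entry. It does not balance groups formed afterwards by an event that treatment may prevent. If CYNK-001 spares milder subjects oxygen or an ICU stay, those subjects leave its arm of the measure and remain in the control arm. The treated users who are left are then sicker on average than the control users, and the summary can show fewer oxygen-free days or a higher SOFA for an effective product.

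The population makes this plausible. Subjects may enter on room air, and the protocol allows Phase II to include outpatients, so some may never need oxygen. Both measures are listed as evidence of overall clinical benefit.

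**Working it through.** The documents give no expected rate, effect or power for these endpoints, so there is no figure of the plan's own to reproduce. Only the 36 per arm and the 28-day window below come from the documents. Every oxygen, ventilation and ICU rate is an assumption.

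**1. Simple case, nobody on oxygen at baseline.** Control: 12 subjects never need oxygen, 12 need it for 10 days, 12 for 20 days. CYNK-001 spares the 10-day group and changes nothing else. Oxygen-free days = 28 minus days on oxygen.

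- Users only: control (12×18 + 12×8)/24 = 13.0; CYNK-001 (12×8)/12 = 8.0; difference −5.0.
- All randomised, never-users scored 28: control (12×28 + 12×18 + 12×8)/36 = 18.0; CYNK-001 (24×28 + 12×8)/36 = 21.3; difference +3.3.

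**2. Weaker effect, and a varying share on oxygen at baseline.** Among control subjects not on oxygen at entry, one third never need it, one third need 5 days and one third need 20. CYNK-001 spares two thirds of the 5-day group. With nobody on oxygen at baseline:

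- Users only: (12×23 + 12×8)/24 = 15.5 against (4×23 + 12×8)/16 = 11.75; difference −3.75.
- All randomised: (12×28 + 12×23 + 12×8)/36 = 19.67 against (20×28 + 4×23 + 12×8)/36 = 20.78; difference +1.11.

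Now let a share of each arm be on oxygen at baseline, needing 14 days in control. The users-only mean is the sum of share × oxygen-free days over users, divided by the share who are users. At 50%, with no effect in baseline users: control (0.5×14 + 0.167×23 + 0.167×8)/0.833 = 14.60; CYNK-001 (0.5×14 + 0.056×23 + 0.167×8)/0.722 = 13.31; difference −1.29.

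Differences in days, CYNK-001 minus control:

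| On oxygen at baseline | Users only, no effect in baseline users | All randomised, same | Users only, 2 days saved in baseline users | All randomised, same |
|---|---|---|---|---|
| 0% | −3.75 | +1.11 | −3.75 | +1.11 |
| 25% | −2.29 | +0.83 | −1.43 | +1.33 |
| 50% | −1.29 | +0.56 | +0.09 | +1.56 |
| 75% | −0.56 | +0.28 | +1.18 | +1.78 |
| 100% | 0.00 | 0.00 | +2.00 | +2.00 |

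The gap between the two analyses closes as the baseline share rises and is zero at 100%.

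**3. Shape of the effect.** A simulation set oxygen days to 6 + 10 × a standard normal severity, rounded and limited to 0 to 28, with no baseline users.

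- Severity lowered by 0.3 SD in everyone: users only 17.24 against 18.60 (+1.36); all subjects 20.37 against 22.36 (+1.99). Both favour treatment, the users-only figure by less.
- Severity lowered by 0.6 SD only in subjects below +0.3 SD: users only 17.24 against 15.05 (−2.19); all subjects 20.37 against 21.78 (+1.41). The sign reverses.

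**4. SOFA.** Suppose 8 of 36 control subjects enter the ICU with scores 4, 4, 4, 5, 8, 9, 10, 10, and CYNK-001 prevents the three admissions with score 4. The ICU-only mean is 54/8 = 6.75 against 42/5 = 8.40, apparently worse, although admissions fall from 8/36 = 22.2% to 5/36 = 13.9%.

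**5. Ventilation wording.** With 6 ventilated per arm in case 1, the denominator implied by protocol 6.9 gives 6/24 = 25% against 6/12 = 50%. The denominator of Table 2 and SAP item 13 gives 6/36 = 16.7% in both arms.

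**The case against.** The best defence is that the plan is explicit and the stakes are low. Its ITT statement yields where something else is specified, and items 12 and 14 do specify a subset. Secondary endpoints carry no formal hypothesis, SOFA is descriptive, and the readable text of SAP 13.3 names no between-arm test for oxygen-free days. The trial stopped in Phase I, and the reduced list in SAP 15 keeps SOFA only if data suffice, in a single arm. All of this stands. It limits the weight of the point but does not make the subset comparison a randomised one.

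A second oxygen measure may also exist. Protocol 6.9 and 11 list oxygen-free days again among organ-support days, and SAP 13.5 summarises organ-support days without naming a population. That does not settle the matter: the protocol nests the list under SOFA, and the SAP does not say who is counted.

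Four stronger readings are tempting, and the documents do not support them:

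- A reader might infer that the oxygen set holds only subjects who start oxygen after randomisation. Subjects on cannula or mask oxygen at entry are eligible and belong to the set.
- A reader might infer that the planned ventilation analysis is biased. SAP items 13 and 13.3 and protocol Table 2 restrict nothing. The fault is conflicting protocol wording.
- A reader might infer that ICU scores are carried forward beyond ICU discharge. SAP 13.3 says only that missing values are imputed. Days after discharge may lie outside the endpoint, so this is an ambiguity.
- A reader might infer that the sign will reverse. Part 3 of the working shows that it need not.

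**Conclusion.** The point holds for two endpoints, oxygen-free days and SOFA. Membership of each set depends on an outcome that treatment can change, so the by-arm summary can understate or reverse a benefit. For SOFA, the entry exclusion means that the set forms essentially after randomisation.

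The size for oxygen depends on two things that the documents do not give: the share on oxygen at baseline, and whether the effect is concentrated in milder subjects. Across the assumed cases in parts 1 and 2, the users-only difference runs from −5.0 to +2.0 days, while the all-randomised difference runs from 0 to +3.3. The ventilation point is a separate inconsistency inside the protocol and leaves the SAP analysis unaffected.

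No between-arm result of this trial was harmed, because none arose. The plan should be corrected before the Phase II design is used again, but the primary analysis does not depend on it.

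**What to change.** 1. In SAP 13.2 item 12 and protocol Table 2, 6.9 and 11, define oxygen-free days to Day 28 in all randomised (ITT) subjects. Score 28 for a survivor who never uses oxygen, and 0 (or the worst rank) for death by Day 28. Without a rule for death, an early death without oxygen could score 28. Keep the users-only table as descriptive, and say which population applies to the organ-support list in protocol 6.9 and 11 and SAP 13.5.
2. Move the ventilation outcome in protocol 6.9 and 11 out from under the conditional heading, so that its denominator is all randomised subjects, as in Table 2 and SAP item 13.
3. Label SOFA within the ICU as descriptive and not a randomised comparison, and state that last observation carried forward is not applied after ICU discharge. If a between-arm ICU comparison is wanted, report ICU admission or death in all randomised subjects.

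The cost is wording, slightly more analysis and a stated convention for deaths. Oxygen start and end days are already needed for NEWS2 (SAP 13.3), and ICU admission is already needed to apply the SOFA definition.

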13.2.1 Exploratory Endpoints

The exploratory outcomes of this study include:

- 1) Cytokine and Chemokine assessment measured serially until Month 6.

- 2) Immune monitoring as measured by chimerism and/or other differentiating methodologies of donor-derived natural killer cells for those treated with CYNK-001. Immune profiling and immunophenotyping including alloreactivity at Month 6.
- 3) Detection of SARS-CoV-2 via rRT-PCR in various specimens including peripheral blood at Month 6.

13.3 Analysis Methods

The primary endpoints will be analyzed with hypothesis testing procedures. No formal hypothesis will be carried out for secondary endpoints and the p-values are provided for informative purpose only.

Missing data and censoring will be handled as described below.

- **Primary Efficacy Analysis**

Phase II efficacy data will be analyzed for the ITT population based on randomized treatment group.

The primary efficacy endpoint is the time to clinical improvement on or before Day 28. Kaplan-Meier estimates of the survival curve, estimate of median survival time and its 95% CI will be calculated. Log-rank test will be used to test the difference between treatment groups while adjusting for pre-defined age strata.

Hazard ratio will be estimated via proportional hazard model using treatment as a factor stratified by age group.

Subjects who withdraw after randomization and before any measurements assessed will be censored at randomization date; subjects who terminate from the study before Day 28 without clinical improvement will be censored on the date of the last visit; and subjects who died without clinical improvement by OSCI will be censored on Day 28; subjects without clinical improvement ~~who have no event~~ on or before Day 28 will be censored on Day 28.

- **Secondary Endpoints Analyses**

The analysis will be based on the ITT population unless otherwise specified. Since the purpose of the analysis is for hypothesis generation, no multiplicity adjustment or adjustments for stratification covariates (age and site strata) will be made.

For the endpoints of event rate, including:

- Proportion of subjects who achieved clinical improvements by OSCI

- Proportion of subjects with clearance of SARS-CoV-2 by rRT-PCR
- Proportion of subjects who had pulmonary clearance by LRT specimens where it has previously been found
- Proportion of subjects who need invasive or non-invasive ventilation
- Proportion of subjects who died

The proportions and their two-side 95% CIs will be calculated. Fisher's exact test will be used to test the difference between treatment groups. If the subject has no data after baseline, the subject will be considered as failure in the analysis.

For endpoints of time to event, including:

- Time to clinical improvement measured by NEWS2 Score
- Time to clearance of SARS-CoV-2 by rRT-PCR testing
- Time to disappearance of virus from LRTI specimen
- Time from randomization to medical discharge
- Duration of hospitalization (from time from hospitalization to medical discharge up to Day 28)

The Kaplan-Meier method will be used for estimating the survival curves, the median survival time and its two-sided 95% confidence interval will be estimated. [REDACTED]

[REDACTED]

Mortality rate will be provided and be compared using Fisher's Exact Test.

For the endpoint of proportion of subjects who achieved clinical symptom improvement by NEWS2 Score by Day 28, clinical improvement is defined as a 25% reduction in NEWS2 Score. The proportions

and their two-sided 95% CIs will be calculated. Fisher's exact test will be used to test the difference between groups. If the subject has no data after baseline, the subject will be considered as failure in the analysis.

1) Calculation

- a. Respiratory rate, oxygen saturation, temperature, systolic blood pressure, and heart rate will be collected on the Vital Signs and Oxygen Saturation eCRF forms.
- b. Consciousness score will be based on the Physical Exam eCRF form. If Neurological is normal, then NEWS2 Consciousness will be scored as zero. If Neurological is abnormal, then the score will be determined based on the comments. A clinical review of the comments from the abnormal neurological findings will be required.
- c. Air or Oxygen will be based on the eCRF form Prior and Concomitant Procedure and Surgeries. If a subject had Preferred Term "Oxygen Therapy" then the NEWS2 Air or Oxygen Score will be 2 for the days from the start day through the end day of the procedure.
- d. Calculation of overall NEWS2 Score for a given day will be the sum of the scores from respiratory rate, oxygen saturation, temperature, systolic blood pressure, heart rate, consciousness, and air or oxygen categories. For infusion days, data for Vital Signs and Oxygen Saturation are collected 3 separate times. For infusion days, a separate overall score will be calculated for each time the Vital Signs and Oxygen Saturation is collected, and the worst overall score will be used as the NEWS2 Score for that day.

2) Missing data handling:

- a. If a measure for vital signs and oxygen saturation is missing, corresponding NEWS2 score will be set as missing, and the overall NEWS2 score takes the form $\geq xx$. If all categories from vital signs and oxygen saturation is missing, the overall NEWS2 score will be set as missing.
- b. If the result for Neurological in Physical Exam is missing or not assessed, then corresponding NEWS2 score will be set as 0.
- c. NEWS2 score for "Air or Oxygen" is based on the presence of oxygen therapy in the prior and concomitant procedure page, so NEWS2 will not be considered as missing.

Ordinal data endpoints, including Clinical status by OSCI and SOFA score, will be summarized descriptively with number and percentage in each treatment arm and overall. LOCF will be used to impute missing data.

